#### 15 Statistics

#### 15.1 Sample size

The primary objective of this study is to determine the relative risk of medially attended wheezing in 28 days following LAIV vaccination compared with placebo. The null and alternate hypotheses are:

H0: Proportion of wheezing LAIV = Proportion of wheezing Placebo

H1: Proportion of wheezing LAIV ≠ Proportion of wheezing Placebo

Where the proportion of wheezing is calculated as the number of participants with respiratory wheezing diagnosed by a health practitioner requiring medical attention within 28 days following receiving LAIV or a placebo. We chose 28 days as this is the common interval to observe intermediate reactions following vaccination. The study was a cross-over design, i.e. participants randomised to LAIV or placebo at Day0 will receive placebo or LAIV at Day28, respectively. Although there is no data on the ideal washout period, it is biologically reasonable to assume that the impact of LAIV will last shorter than 28 days. The data from a previous publication comparing medically significant wheeze rates between LAIV and inactivated vaccine groups reported 44 vs 20 cases in the first 28 days following vaccination, and 11 vs 14 cases between 29-42 days post-vaccination, further supporting our assumption. Therefore, we will use both Day 0-28 and Day 28-56 periods in the primary analysis in the primary analysis.

The sample size calculation is based on the below assumptions:

- 1. The proportion of medially attended wheezing is 0.9% following placebo in 28 days following vaccination;
- 2. The relative risk of interest is 2;

- 3. Study power of 80%;
- 4. Type I error of 0.05 two-sided;

Based on the above sample size, the study will need to recruit 2800 effective participants. Given the study endpoint will be extracted based on electronic medical records, we expect the attrition rate will be low. The total sample size will be 3000.

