## 8 Risks and Benefits

## 8.1 Potential benefits

Participants in the study will receive a vaccine against seasonal influenza which otherwise will not be available to them through the national immunisation programme. Receipt of the vaccine may provide immune protection against the circulating strains of influenza during this autumn/winter season.

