#### 15.2 Description of statistical methods

The primary analysis population will be participants who are randomised and received LAIV or placebo at Day 0 and Day 28. The proportion of participants with a diagnosis of medically attended wheezing between Day 0 to Day 28 and between Day 28 and Day 56, along with the associated 95% confidence intervals will be presented. When calculating the proportion, the numerator will be the number of participants randomised and received LAIV or placebo at the start of each period. The analysis will be conducted according to the vaccine received. The difference in proportions between the two arms will be analysed using Pearson's chi-squared test after combining the data from both periods. The corresponding 95% CI will be derived using a standard method. The risk of wheezing following LAIV will be estimated by a mixed-effects model with the study vaccine received at the start of each period, study period (months) and sequence as fixed effects and participant ID as a random effect to account for within-subject variability. The Kaplan-Meier curve will be used to visualise the time to medically attend wheeze. Participants who withdrew from the study will be censored in the analysis at the time of withdrawal. Non-diagnosed participants will be censored in the analysis at 28 days following vaccination in both periods.

Carryover effects were assessed by testing for the interaction between vaccine and sequence, and if significant, the comparison between the two groups will be done for the two periods separately. We will also test the interaction between the study period (by months) and the vaccine to understand if any increased risk observed following LAIV is affected by the background wheezing risk.

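### About half of the pooled saline time follows LAIV, the washout support does not show that time is clean, and 15.2 makes the carry-over-free first-period comparison conditional on a weak test

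*Protocol*

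**What the plan says.** Under Protocol 10.1.4 the early-vaccine group receives LAIV on day 0 and saline on day 28. Allocation is 1:1 (section 3), so about half of all saline follow-up is days 28-56 after LAIV. There is no separate washout interval.

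Section 15.1 concedes that the ideal washout is unknown, then argues that "it is biologically reasonable to assume that the impact of LAIV will last shorter than 28 days". The only data offered come from a publication "comparing medically significant wheeze rates between LAIV and inactivated vaccine groups reported 44 vs 20 cases in the first 28 days" and 11 vs 14 on days 29-42. On that basis both periods enter the primary analysis. Section 15.2 pools them in a chi-squared test and adds a mixed-effects model.

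Three other statements bear on the point:
- 8.1 lists as a potential benefit: "Receipt of the vaccine may provide immune protection against the circulating strains of influenza during this autumn/winter season".
- 15.2 presents the proportion with wheeze, with confidence intervals, for each period without condition.
- 15.2 also tests for carry-over and, "if significant, the comparison between the two groups will be done for the two periods separately".

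**The concern.** The pooled placebo risk mixes two kinds of saline time: children who have not had LAIV in the trial, and children who had it 28 days earlier. If LAIV still affects wheeze after day 28, the mixture is no longer the background risk, and the pooled relative risk moves away from the 28-day effect. Remaining protection lowers the placebo risk and makes LAIV look worse. Remaining provoked wheeze raises the placebo risk and makes LAIV look safer, which is the more serious error in a trial set up to detect harm.

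Only days 0-28 compare LAIV with saline in children not yet vaccinated in the trial. Section 15.2 makes the group comparison for that period depend on the result of a test, so it may not be reported in the case where carry-over is present but undetected.

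**Working it through.** **Inputs (15.1).** "The proportion of medially attended wheezing is 0.9% following placebo in 28 days following vaccination"; "The relative risk of interest is 2", so 1.8% after LAIV; power 80%; "Type I error of 0.05 two-sided"; 2800 effective participants, 3000 in total.

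**1. The plan's own figure.** With p1 = 0.009, p2 = 0.018 and mean 0.0135:

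n = [1.96 × √(2 × 0.0135 × 0.9865) + 0.842 × √(0.009 × 0.991 + 0.018 × 0.982)]² / 0.009² = 2580 per condition.

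With continuity correction: (2580/4) × [1 + √(1 + 4/(2580 × 0.009))]² = 2798.

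This reproduces 2800, provided each child supplies one LAIV and one saline period and these are treated as independent. The uncorrected power with 2800 per condition is 83%.

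**2. What the cited counts show.** The protocol gives no denominators, so equal arms are assumed.
- Days 29-42: 11/14 = 0.79. SE of the log ratio = √(1/11 + 1/14) = 0.403. 95% CI = 0.79 × exp(±1.96 × 0.403) = 0.36 to 1.73. The exact interval is 0.32 to 1.86.
- Change between windows: (44/20)/(11/14) = 2.2/0.786 = 2.8. SE = √(1/44 + 1/20 + 1/11 + 1/14) = 0.485. 95% CI 1.08 to 7.24, treating events as independent.

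The ratio therefore fell after day 28, with borderline evidence. Where it settled is poorly known. Because both arms had received an influenza vaccine, an effect common to both, such as protection from influenza, cancels in this ratio.

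**3. Effect on the pooled estimate.** Let k be the rate ratio in the early-vaccine saline period relative to background. Assume the same background in both periods, equal groups and 2800 children with both periods complete. Then pooled placebo risk = 0.9% × (1 + k)/2, and the relative risk read = true relative risk / [(1 + k)/2]. The values of k are illustrative.

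| k | Pooled placebo risk | True RR 1 reads | True RR 2 reads | Power at true RR 2 |
|---|---|---|---|---|
| 0.80 | 0.81% | 1.11 | 2.22 | 90% |
| 0.95 | 0.88% | 1.03 | 2.05 | 85% |
| 1.00 | 0.90% | 1.00 | 2.00 | 83% |
| 1.20 | 0.99% | 0.91 | 1.82 | 73% |
| 1.50 | 1.125% | 0.80 | 1.60 | 56% |

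**4. Power of a carry-over test.** In a two-period, two-sequence design, carry-over appears in the contrast between sequence totals. The vaccine-by-sequence product named in 15.2 coincides with the first-versus-second-period contrast, so I evaluate the sequence contrast. With 1400 children per sequence and a true relative risk of 2, the difference in expected totals is 0.009 × (k − 1).
- k = 1.5: difference 0.0045, SE = √[(0.018 × 0.982 + 0.0135 × 0.9865 + 0.018 × 0.982 + 0.009 × 0.991)/1400] = 0.0064. Power about 11%.
- k = 2: difference 0.009, SE 0.0067. Power about 27%.

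**5. First period alone, true relative risk 2.** Power is 54% with 1400 per arm and 57% with 1500 per arm (no continuity correction).

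**The case against.** The case for the plan has real content.

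- *A reader might infer that 8.1 contradicts 15.1.* It does not clearly do so. Section 8.1 says only that protection may occur, and the washout sentence sits among remarks on reactions and wheeze counts, so impact can mean provoked wheeze alone. Both statements can be true. What stands is that 15.1 does not say which meaning it intends, and the difference matters because the Lay Summary links wheeze in young children to many respiratory viruses.
- *A reader might infer that the cited data give no support.* They give some: the fall from 2.2 to 0.79 is what a fading excess would look like, and 15.1 offers it as further support, not as proof.
- *A reader might infer that the first period will stay hidden unless carry-over is significant.* Section 15.2 promises proportions with intervals for each period, and the Lay Summary describes a comparison in each four-week block without condition. What remains conditional is the formal group comparison by period.
- *A reader might take the limits of the cited interval as the plausible range for k.* At 1.73, power would fall to about 42%. But that ratio is against an active vaccine over days 29-42, so it does not estimate k against saline over days 28-56, and its point estimate lies on the other side of 1.

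Supportive estimates are often left to the SAP, which is not shown. Here, though, the protocol itself fixes the pooling, the washout argument and the significance trigger.

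**Conclusion.** The point holds as a cheap improvement, not as a fault that invalidates the design. About half of the pooled saline time rests on an assumption that the cited data support in direction but do not establish, because of the active comparator, the end at day 42 and the imprecision. The test meant to guard the assumption would miss a residual ratio of 1.5 to 2 in roughly 73 to 89% of trials.

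The size of the bias is unknown, because the protocol gives neither influenza's share of wheeze nor any LAIV-versus-saline data beyond day 28. Modest residual protection (k of 0.8 to 0.95) would shift the pooled relative risk up by about 3 to 11%, an error in the cautious direction. Residual harm at k = 1.5 would be material. These figures assume equal groups, a constant background and independent periods. They do not show that carry-over exists, and they do not justify abandoning the pooled analysis.

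**What to change.** Keep the cross-over and the pooled primary analysis.

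- **15.2:** remove the rule that makes the separate-period comparison depend on a significant carry-over test. State instead that the LAIV-versus-saline relative risk for days 0-28, with its 95% CI, is always reported beside the pooled estimate as a pre-specified supportive result. This also brings 15.2 into line with the Lay Summary.
- **15.1:** say whether the impact assumed to end within 28 days is provoked wheeze only or any effect on wheeze, including protection. Add that the cited comparison was with an inactivated influenza vaccine, ended at day 42 and is imprecise.
- Do not make the pooled result valid only when it is compatible with the first period. Compatibility would be undefined, and such a rule would again depend on the data.

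The cost is a few sentences and one extra estimate, with no change to any child's treatment or visits. The downside is a wider first-period interval (about 54 to 57% power alone at a relative risk of 2), so it should be labelled supportive.

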#### 15.2 Description of statistical methods

The primary analysis population will be participants who are randomised and received LAIV or placebo at Day 0 and Day 28. The proportion of participants with a diagnosis of medically attended wheezing between Day 0 to Day 28 and between Day 28 and Day 56, along with the associated 95% confidence intervals will be presented. When calculating the proportion, the numerator will be the number of participants randomised and received LAIV or placebo at the start of each period. The analysis will be conducted according to the vaccine received. The difference in proportions between the two arms will be analysed using Pearson's chi-squared test after combining the data from both periods. The corresponding 95% CI will be derived using a standard method. The risk of wheezing following LAIV will be estimated by a mixed-effects model with the study vaccine received at the start of each period, study period (months) and sequence as fixed effects and participant ID as a random effect to account for within-subject variability. The Kaplan-Meier curve will be used to visualise the time to medically attend wheeze. Participants who withdrew from the study will be censored in the analysis at the time of withdrawal. Non-diagnosed participants will be censored in the analysis at 28 days following vaccination in both periods.

Carryover effects were assessed by testing for the interaction between vaccine and sequence, and if significant, the comparison between the two groups will be done for the two periods separately. We will also test the interaction between the study period (by months) and the vaccine to understand if any increased risk observed following LAIV is affected by the background wheezing risk.

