## 12.4 Blinding and code-breaking

Participants' parents/legal guardians and analysing statisticians will remain blind to treatment allocation. Clinical staff involved in study delivery will be aware of which vaccine the participant is receiving (arm allocation). To maintain blinding as much as possible from attending healthcare providers during the study, arm allocation will be concealed from other healthcare provider contacts via the electronic case report form and will only be visible to site staff at the time data is being entered during a vaccination visit.

If the clinical condition of a child necessitates unblinding to vaccine or placebo allocation, the local investigator will have unrestricted and immediate access to break the treatment code via the participants electronic case report form if they find it is in the best interest of the trial subject. This will be done if unblinding is thought to be relevant and likely to change clinical management.

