## 12.6 Early Discontinuation/Withdrawal of Participants

In accordance with the principles of the current revision of the Declaration of Helsinki and any other applicable regulations, a participants' parents/legal guardian has the right to withdraw them from the study at any time and for any reason, and are not obliged to give their reasons for doing so. The Investigator may withdraw the participant at any time in the interests of the participants' health and well-being. In addition, the participant may withdraw/be withdrawn for any of the following reasons:

- Administrative decision by the Investigator
- Ineligibility (either arising during the study or retrospectively, having been overlooked at screening).
- Significant protocol deviation

- Participant non-compliance with study requirements
- An AE, which requires discontinuation of the study involvement or results in inability to continue to comply with study procedures

The reason for withdrawal will be recorded in the CRF. If withdrawal is due to an AE, appropriate follow-up visits or medical care will be arranged, with the agreement of the volunteer, until the AE has resolved, stabilised or a non-trial related causality has been assigned. The DSMB or DSMB chair may recommend withdrawal of participants.

In cases of subject withdrawal, long-term safety data collection may continue as appropriate if subjects have received one or more vaccine doses, unless they decline any further follow-up.

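### The primary population, read plainly, requires both products, so first-period wheeze in a child not dosed at Day 28 is left out; the next sentence conflicts with this and mislabels the denominator

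*Protocol*

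**What the plan says.** Section 15.2 of the protocol defines the population: "The primary analysis population will be participants who are randomised and received LAIV or placebo at Day 0 and Day 28". It then says: "When calculating the proportion, the numerator will be the number of participants randomised and received LAIV or placebo at the start of each period". Further on, after the Kaplan-Meier curve is introduced, it adds: "Participants who withdrew from the study will be censored in the analysis at the time of withdrawal".

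Section 15.1 brings both periods into the main comparison ("Therefore, we will use both Day 0-28 and Day 28-56 periods in the primary analysis") and defines the endpoint as wheeze within 28 days of receiving either product, without any condition on a second dose. The lay summary (section 4) likewise describes the first comparison as one between the 1500 children given vaccine and the 1500 given placebo at the start.

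Section 12.6 lists reasons for withdrawal. They include parental choice, ineligibility that arises during the study, and "An AE, which requires discontinuation of the study involvement or results in inability to continue to comply with study procedures". The same section says that safety data collection may continue after one or more doses unless the family declines. Section 12.4 states that "Clinical staff involved in study delivery will be aware of which vaccine the participant is receiving", while parents are blinded.

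**The concern.** Receipt of the Day-28 product happens after randomisation and after the whole first observation period. A child who wheezes in that period can be withdrawn before Day 28 by any of the routes in section 12.6. If the primary set requires both products, that child's event is excluded from the comparison it was meant to inform, even where it was recorded.

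The loss may also differ by arm. The second product is saline in the early-vaccine arm and live vaccine in the late-vaccine arm, and delivery staff know which is due. Any difference in how often wheezers go on to the second product then enters the relative risk directly.

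The following sentence does not settle the matter. If it means dosed at the start of the period in question, it contradicts the population sentence; if it means dosed at both starts, it repeats the restriction. Either way it names the number of children dosed as the numerator of the proportion, which is wrong.

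**Working it through.** **Inputs from section 15.1:** placebo risk 0.9% in 28 days; relative risk 2, so 1.8% on LAIV; two-sided alpha 0.05; power 80%; 2800 effective participants; 3000 in total. Allocation is 1:1 (section 3).

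**The plan's own figure.** The pooled two-proportion formula gives 2580 per condition without continuity correction. With the correction, n/4 × (1 + √(1 + 4/(n·d)))², where n = 2580 and d = 0.009:
2580/4 × (1 + √1.172)² ≈ 2798.
This matches 2800 when each child counts once under LAIV and once under placebo. The sample size is therefore not in question here, and it assumes that both periods are used.

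**Expected events, 2800 children (1400 per sequence).** Each period gives 1400 × 0.018 = 25.2 LAIV events and 1400 × 0.009 = 12.6 placebo events. Over both periods that is 50.4 and 25.2, about 76 in all.

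**Effect of the both-doses rule.** Let a and b be the shares of first-period LAIV and placebo wheezers who do not receive the second product. Then
- LAIV events = 25.2(1 − a) + 25.2
- placebo events = 12.6(1 − b) + 12.6
- pooled RR = 2 × (2 − a)/(2 − b)
- first-period RR = 2 × (1 − a)/(1 − b).

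The small change in the denominators is ignored. Allowing for it, and for the missing second periods, moves 1.84 only to 1.85. Power is for the chi-squared test without continuity correction, at 2800 and at 3000 children per condition, with the two periods treated as independent samples. Starting from 3000 assumes no other loss.

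| Assumed a, b | LAIV / placebo events (2800) | Pooled RR | First-period RR | Power, 2800 | Power, 3000 |
|---|---|---|---|---|---|
| 0, 0 | 50.4 / 25.2 | 2.00 | 2.00 | 83% | 86% |
| 20%, 20% | 45.4 / 22.7 | 2.00 | 2.00 | 79% | 82% |
| 25%, 10% | 44.1 / 23.9 | 1.84 | 1.67 | 69% | 72% |
| 10%, 25% | 47.9 / 22.1 | 2.17 | 2.40 | 88% | 90% |

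The higher power in the last row comes from an estimate biased upwards; it is not a gain.

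**Loss unrelated to wheeze.** If the whole allowance of 200 in 3000 (6.7%) is Day-28 non-dosing unrelated to wheeze, then among 1500 children per sequence about 27.0 × 0.067 = 1.8 LAIV and 13.5 × 0.067 = 0.9 placebo first-period events are lost. That is 2.7 of 40.5, and the relative risk stays at 2.00.

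**Under a per-period rule** all first-period events are kept. The expected relative risk is then 2.00 in every row, provided second-period risk does not depend on first-period wheeze. The required sample size does not change.

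**The case against.** The strongest reply is that the text can be read as an as-treated, per-period population. Two products are given at the starts of two periods, the proportions are based on children dosed at the start of each period, and the mixed model uses the product received at the start of each period and can use an incomplete pair. That reading is possible. It is not what the population sentence plainly says, and no other sentence states that a child dosed once enters the primary comparison. The censoring sentence follows the Kaplan-Meier display and does not widen the population. So the reply stands as evidence of ambiguity, not as an answer.

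A reader might infer that the children harmed enough to stop are the ones removed, and that the rule hides harm. The documents do not support that. No stated rule withholds the second product after a wheeze: the temporary exclusions in section 11.3.1 are written for Visit 1 only, and the adverse-event reason in section 12.6 is narrower than any medically attended wheeze. Blinding of parents removes one source of differential refusal. If unblinded staff were more hesitant where the remaining product is live vaccine, the extra loss would fall on placebo wheezers, which inflates the relative risk. The direction is open.

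It is also fair that the protocol expects low attrition and that 200 children are allowed for it, so equal loss of 20% among wheezers still leaves about 82% power starting from 3000. Low overall attrition is only partial reassurance, however: with about 38 expected first-period events among 2800 children, a handful of missing wheezers moves the estimate.

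The mislabelled numerator is a separate wording error, and section 15.1 makes the intended count clear. It would be too much to say that the analysis will be computed wrongly because of it.

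**Conclusion.** The defect is real and its size is unknown. On its plain reading, the primary safety population is conditioned on a post-randomisation event that the primary outcome can influence. The adjoining sentence leaves the rule in doubt and mislabels the denominator.

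Bias in the relative risk needs non-dosing among wheezers that differs by product. At an assumed 25% against 10%, a true relative risk of 2.0 is estimated as 1.84 or 2.17, depending on direction. Because section 15.2 moves to separate periods if the carryover test is significant, the first-period values of 1.67 or 2.40 could become the ones that matter. Equal or unrelated loss costs events and precision only. All non-dosing rates are assumptions, and the protocol offers none to replace them. This should be fixed; the documents do not show that the primary result will be materially wrong.

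**What to change.** Change two sentences in section 15.2:

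1. State that the primary analysis includes every randomised child who received at least one product, and that each child contributes every period in which a product was given, whether or not the other period was reached. Use the outcome data available under the consent still in force.
2. For each product, define the numerator as children with medically attended wheeze within 28 days of receiving it, and the denominator as children given it.

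Keep the both-doses set as a sensitivity analysis, and carry the same definitions into any statistical analysis plan.

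The cost is small: no new visits, no change in sample size, and outcomes already come mainly from GP records. Two limits remain. After withdrawal, collection only may continue and stops if the family declines, so some first-period events may still be unavailable. And children who are not dosed again are absent from the second period under any rule, so the number not dosed at Day 28 should be reported by arm and by first-period wheeze.

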#### 11.3 Exclusion Criteria

The participant may not enter the trial if ANY of the following apply:

- Previous receipt of an IM seasonal influenza vaccine
- Receipt of any investigational vaccine other than the study intervention within 30 days before
  and after each study vaccination.
- Living in close contact with someone with a severely weakened immune system.
- Administration of immunoglobulins and/or any blood products within the three months
  preceding the planned administration of the vaccines.
- Children eligible for annual influenza immunisation according to the national NHS programme, including those with any confirmed or suspected immunosuppressive or immunodeficient state; asplenia; recurrent severe infections and use of immunosuppressant medication within the past 6 months, except topical steroids or short-term oral steroids (course lasting ≤14 days).

- History of allergic disease or reactions likely to be exacerbated by any component of study
  vaccines (e.g. hypersensitivity to gentamicin, gelatin, or other ingredients of Fluenz). Allergy
  to egg is only a contraindication if the participant has previously had anaphylaxis to egg.
- Any history of anaphylaxis.
- Current diagnosis of or treatment for cancer
- Any other significant disease, disorder or finding which may significantly increase the risk to
  the volunteer because of participation in the study, affect the ability of the volunteer to
  participate in the study or impair interpretation of the study data.
- Severe and/or uncontrolled cardiovascular disease, respiratory disease, gastrointestinal
  disease, liver disease, renal disease, endocrine disorder and neurological illness, defined
  broadly as currently requiring frequent hospital/specialist input or recently resulting in
  hospital admission, or as determined by the investigator (mild/moderate well controlled
  comorbidities are allowed).
- History of active or previous auto-immune neurological disorders (e.g. Guillain-Barre syndrome, transverse myelitis).
- Scheduled elective surgery during the trial
- Children receiving salicylate therapy (i.e., aspirin)
- Participants who have received an investigational product, or participated in another research trial involving an investigational product in the past 12 weeks or 5 half-lives after the last IMP dose (whichever is longer) before the first dose of study treatment.

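### Section 15.2 restricts the primary population to children dosed at both visits, so a recorded first-period wheeze drops out if the second dose is not given, and the section's own counting rules conflict with this

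*Protocol*

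**What the plan says.** Section 15.2 fixes the primary population in one sentence: "The primary analysis population will be participants who are randomised and received LAIV or placebo at Day 0 and Day 28". Two later sentences in that section work differently. For the proportions, "the numerator will be the number of participants randomised and received LAIV or placebo at the start of each period" (the denominator is evidently meant). After the Kaplan-Meier sentence it adds: "Participants who withdrew from the study will be censored in the analysis at the time of withdrawal".

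Section 12.6 lists ways a child may leave before the second dose. They include "Ineligibility (either arising during the study or retrospectively, having been overlooked at screening" and "An AE, which requires discontinuation of the study involvement or results in inability to continue to comply with study procedures". A parent may also withdraw the child at any time without giving a reason. Section 12.6 allows safety data collection to continue after withdrawal once a dose has been given, so the first-period outcome may be fully known for such a child.

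Section 15.1 says both periods enter the primary analysis and sets no requirement that a child complete both.

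**The concern.** A population defined by receipt of the second dose conditions on something that happens after randomisation and after the first-period endpoint window, and the endpoint itself can influence it. Suppose a child wheezes on day 10, the event is extracted from the GP record, and for any of the section 12.6 reasons no dose follows at Day 28. Under the literal definition that observed primary event is not analysed. Section 15.4 on missing data does not help, because nothing is missing.

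Wheeze safety is the purpose of the trial and events are few. If wheezers miss the second dose more often than other children, the absolute risks and the risk difference are understated and power is lost. If the excess is larger after live attenuated influenza vaccine (LAIV) than after placebo, the relative risk (RR) also moves towards 1.

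**Working it through.** **The three rules side by side.** Take a child dosed at Day 0, wheezing on day 10, withdrawn on day 15 and not dosed at Day 28.

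- Population sentence: the child and the event are excluded.
- Per-period count: the child was dosed at the start of period 1, so child and event are included in that period.
- Censoring rule: the child is followed to withdrawal, so the day-10 event is included.

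The rules give different answers for the same child, and no sentence says which prevails.

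**Inputs.** Section 15.1: placebo 28-day risk 0.9%, RR 2 (so 1.8% after LAIV), two-sided 5%, power 80%, 2800 effective and 3000 total. Protocol Summary: 1:1 allocation, so 1500 per sequence. Assumed, because the protocol gives no figure: 5% of first-period non-wheezers are not re-dosed; a share h_L of first-period wheezers after LAIV and h_P after placebo are not re-dosed; second-period risks equal the planning rates.

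**The plan's own figure.** The two-proportion formula with pooled variance and continuity correction, 0.9% vs 1.8%, gives 2798 per treatment. Each child counts once under each treatment, so the stated 2800 reproduces. Without the correction the formula gives 2580. Power with 3000 children, uncorrected, is 85.6%.

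**Events exposed.** Period 1: 1500 × 0.018 = 27 after LAIV and 1500 × 0.009 = 13.5 after placebo, together 40.5. Both periods: 3000 × 0.018 + 3000 × 0.009 = 54 + 27 = 81. Half the events are exposed.

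**Both-doses rule.** In each sequence, with first-period risk p:

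- wheezers kept = 1500 × p × (1 − h)
- non-wheezers kept = 1500 × (1 − p) × 0.95
- first-period risk = wheezers kept / (wheezers kept + non-wheezers kept)

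Second-period events = children kept × planning risk. Power uses the uncorrected two-proportion formula on the pooled periods, treating the two periods as independent.

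Worked case, h_L = h_P = 50%:

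- LAIV first: 27 × 0.5 = 13.5 wheezers and 1500 × 0.982 × 0.95 = 1399.35 others, total 1412.85. Risk 13.5/1412.85 = 0.96%.
- Placebo first: 6.75 wheezers and 1500 × 0.991 × 0.95 = 1412.175 others, total 1418.925.
- Pooled LAIV: (13.5 + 1418.925 × 0.018)/2831.8 = 1.379%. Pooled placebo: (6.75 + 1412.85 × 0.009)/2831.8 = 0.687%.
- RR 2.01, risk difference 0.69 points, power 73%.

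| Wheezers not re-dosed (LAIV / placebo) | Events dropped | First-period LAIV risk | Pooled RR | Pooled risk difference (points) | Power | Children left |
|---|---|---|---|---|---|---|
| 5% / 5% | 2.0 | 1.80% | 2.00 | 0.90 | 84% | 2850 |
| 10% / 10% | 4.1 | 1.71% | 2.00 | 0.88 | 83% | 2848 |
| 20% / 20% | 8.1 | 1.52% | 2.00 | 0.83 | 81% | 2844 |
| 50% / 50% | 20.3 | 0.96% | 2.01 | 0.69 | 73% | 2832 |
| 10% / 5% | 3.4 | 1.71% | 1.95 | 0.85 | 80% | 2849 |
| 40% / 20% | 13.5 | 1.14% | 1.78 | 0.64 | 62% | 2839 |

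**Per-period rule, same losses.** All first-period events stay. RR is 2.00 and power about 85% in every row, because a missed second dose costs only the second period.

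**The case against.** **The sentence may simply name the two dosing occasions.** On that reading it requires a dose at whichever visit opens a period, and the per-period count and the censoring rule agree with it. This is a fair reading of the intent. It does not settle the text: the ordinary meaning requires both doses, and nothing gives the other sentences precedence.

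**Severe cases as the likeliest losses.** A reader might infer this from section 12.6 together with the section 11.3 criterion on respiratory disease, "broadly as currently requiring frequent hospital/specialist input or recently resulting in" hospital admission. The documents do not support going that far. Section 12.6 is permissive and does not mention wheeze. The section 11.3 criterion concerns severe or uncontrolled disease and governs entry. The temporary exclusions in section 11.3.1 apply to Visit 1, and no written rule withholds the Day 28 dose after wheeze. Children with earlier wheeze are deliberately invited. Under section 9.1 a GP code or a new bronchodilator prescription is enough for an event, so many events need not be severe.

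**The attrition argument.** Section 15.1 says: "Given the study endpoint will be extracted based on electronic medical records, we expect the attrition rate will be low". Record extraction does not secure Day 28 attendance, so a reader might conclude that the sample size fails. That is not shown. The step from 2800 to 3000 allows 200/3000 = 6.7%, and every scenario above leaves more than 2800 children.

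**A study pause.** One might infer that a pause running past the Day 28 window would remove all children then between doses. Section 15.2 does not make the visit window a condition of membership.

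**The events stay in the trial.** Serious and medically attended adverse events are secondary outcomes throughout, and the safety board sees safety data. This stands; only the primary comparison is affected.

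**Conclusion.** The point holds as a badly fixed and internally inconsistent population definition that should be corrected. Taken literally, section 15.2 removes observed first-period events from the primary safety analysis when the second dose is not given, and it conflicts with two other rules in the same section.

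The size cannot be read from the protocol. If wheezers and other children miss the second dose equally often (5%), the cost is about 2 events and one point of power. If wheezers miss it more often but equally after LAIV and placebo, absolute risk and power fall and the RR does not. Masking of a relative increase needs heavier loss after LAIV than after placebo, which is possible but for which the documents give no evidence. The 40% vs 20% row therefore illustrates sensitivity and is not a forecast.

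**What to change.** In section 15.2 replace the population sentence with: *The primary population is, for each period, all randomised children who received LAIV or placebo at the start of that period; a child dosed only at Day 0 contributes the first period.* Use this set for the proportions, the chi-squared test, the mixed-effects model and the Kaplan-Meier curve. Keep the both-doses set as a sensitivity analysis. In the same edit, change numerator to denominator in the proportion sentence.

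The cost is a few sentences of wording. First-period outcomes are already collected, and both the pooled proportions and the mixed-effects model can take children who contribute one period. If a per-period population was intended all along, the analysis does not change.
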